### **5.3.3 Exclusion Criteria**

#### **5.3.3.1 General Exclusion Criteria**

Potential subjects required for study participation must not meet any of the following exclusion criteria to be enrolled in the study:

1. Stand-alone AF without indication(s) for concomitant CABG and/or valve surgery.
2. Previous left sided ablation procedures prior to surgical ablation.
3. Untreated atrial flutter and symptomatic ventricular arrhythmia.
4. Known carotid artery stenosis greater than 80% prior to index ablation procedure.
5. Prior history of ischemic stroke or hemorrhagic stroke.
6. History of MI with ST elevation within 6 weeks prior to the index ablation
7. Documented AF duration of greater than 10 years.
8. Large left atrial size i.e., LA diameter  $>7$  cm prior to the index ablation procedure.
9. Subjects with active systemic infection prior to index ablation procedure.
10. Subjects who had documented severe peripheral arterial occlusive disease defined as claudication with minimal exertion prior to the ablation procedure.
11. Subjects with history of renal failure requiring dialysis or hepatic failure prior to the ablation procedure.
12. A known drug and/or alcohol addiction.
13. Mental impairment or other conditions which may not allow the subject to understand the nature, significance, and scope of the study.
14. Subjects who are pregnant.
15. Subjects who had preoperative need for mechanical circulatory support or intravenous inotropes.
16. Subjects who are on anti-arrhythmic drug therapy for the treatment of another arrhythmia.
17. Subjects in currently undergoing chemotherapy.
18. Subjects on long term treatment with oral or injected steroids (not including intermittent use of inhaled steroids for respiratory diseases).
19. Subjects who had known connective tissue disorders at the time of index ablation procedure.
20. Subjects who had known hypertrophic obstructive cardiomyopathy at the time of index ablation procedure.
21. Subjects with known cold agglutinin.
22. Subjects who had or tested positive for COVID-19.
23. Subjects with bleeding disorders and/or inability to receive anticoagulation
24. Subjects undergoing aortic dissection surgery as index procedure.
25. Cardiac surgical re-intervention since the index cardiac surgery with concomitant AF ablation procedure.

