#### **5.2 Subject Screening and Informed Consent**

##### **5.2.1 Subject Screening**

Potential subjects presenting at the clinical sites will be fully informed about the clinical investigation, following the established Informed Consent process (described in [Section 5.2.2]).

Subjects must be screened for clinical investigation eligibility by a member of the site's clinical investigation team previously trained to the protocol, and if applicable will be entered into a site-specific screening log.

In case the subject does not meet all inclusion criteria or meets any of the exclusion criteria, the subject is considered a screening failure. The Principal Investigator or the delegated clinical

investigation personnel will record the reasons for screen failure (e.g. inability to consent, refusal to consent, did not meet inclusion/exclusion criteria, death or major morbidity (such as stroke) etc.) on a screening log within the EDC as required.

Subjects meeting general inclusion criteria and no exclusion criteria will be asked to sign an Informed Consent form if they wish to participate in the clinical investigation. These subjects will also be entered into the screening log.

Subject data will be collected following enrollment into the clinical investigation and will be based on random selection of treated subjects.

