## **6 TREATMENT AND EVALUATION OF ENDPOINTS**

### **6.1 Study Eligibility**

All subjects recruited for study enrollment must meet all study enrollment criteria prior to being enrolled in the study. The clinical investigation site will review all subjects treated with the CRYOF surgical ablation system, and who are within 24-months post-procedure for study eligibility. Once the initial chart review indicates that the subject meets the study inclusion / exclusion criteria, the subject will be approached for their interest in the study, including willingness to return for their follow-up visit.

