### **6.2 Follow-up Assessments**

#### **6.2.1 12-Month Visit ( $\geq$ 12-months but $\leq$ 24-months post index ablation procedure)**

Subjects will be consented 12 to 24 months post procedure and will be provided with a 24-Hour rhythm monitoring device at that time. The post procedure follow-up assessment will include:

- NYHA Classification
- 24-Hr Rhythm Assessment
- Evaluation of AEs/SAEs
- Medications – class I and III AAD's and anticoagulants, including any adjustments
- Review cardioversion since last visit

Note: If a clinical site is capable of remote subject visits, a modified visit assessment may be conducted. Remote subject visits should include Telemedicine appointments with the Investigator, where feasible, to allow direct engagement with the study subject and to ensure complete data collection. Rhythm monitoring devices may be provided to the subject either during an in-clinic follow-up visit, or shipped to the subject for a remote follow-up visit as applicable.

If clinical site is NOT able to perform remote subject visits, an attempt will be made to schedule the study subject visit as close to the visit window as is possible.

Regardless of when the subject is consented, the following data will be collected by reviewing the subjects' medical records retrospectively. For retrospective visits that fall outside of the required windows, please refer to sections 6.2.9 (Unscheduled Visit) and 10.6 (Protocol Deviations).

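### Exclusion 5 and the screen-failure wording let sites screen out, after surgery, a patient whose post-operative stroke is itself a primary safety event; exclusions 16 and 3 lack a time anchor too, with a less certain or narrower effect.

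*Combined protocol and SAP*

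**What the plan says.** **When eligibility is judged.** Section 6.1 has sites review patients already treated with the device and within 24 months of surgery. They are approached "Once the initial chart review indicates that the subject meets the study inclusion / exclusion criteria". Section 5.3.1 bases the assessment on site records and a candidate interview, and any exclusion that is met bars enrolment. Section 6.2.1 fixes the time of consent: "Subjects will be consented 12 to 24 months post procedure".

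**The exclusions (Section 5.3.3.1, repeated in the Synopsis).**
- No. 3: "Untreated atrial flutter and symptomatic ventricular arrhythmia". No date.
- No. 5: "Prior history of ischemic stroke or hemorrhagic stroke". Prior to what is not stated.
- No. 16: "Subjects who are on anti-arrhythmic drug therapy for the treatment of another arrhythmia". Present tense, no date.
- For contrast, no. 4: "Known carotid artery stenosis greater than 80% prior to index ablation procedure".

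**Screening log.** Section 5.2.1 gives as screen-failure reasons, among others, "did not meet inclusion/exclusion criteria, death or major morbidity (such as stroke) etc". Section 3.1 has an equivalent list.

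**Endpoints.** Under Section 4.1, stroke of any level of disability, if related to the ablation procedure and within 30 days, is a primary safety event. Under Section 4.2, AF, flutter or atrial tachycardia over 30 seconds at the last visit is a primary performance failure. So is use at that visit of a new Class I or III drug, or of a dose above one that previously failed.

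**The concern.** In a study that enrols after the outcome window has opened, an eligibility rule without a reference date can act on the outcome itself. A stroke on day 5 is history by the time the chart is reviewed at month 12 or later. If the site applies no. 5 as of screening, or simply uses the stroke reason offered by the log, the patient leaves both numerator and denominator of the MAE rate.

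Nothing later in the plan brings that patient back. The ITT set in Section 8.1 is defined by device use, but study data are collected only after consent and enrolment (Sections 5.1 and 5.4). Random invitation order (Section 3.2) does not help, because ineligible patients are still removed. The missing-data analyses in Section 8.8 are not set up to cover people who never entered the study.

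Both primary tests are single-arm comparisons with fixed goals, and both must pass (Section 8.10). There is no control arm in which the same selection could cancel.

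**Working it through.** **1. The plan's own figures.** Exact one-sample binomial, using the rules in Section 8.3.
- Performance: goal 55%, expected 68%, n = 140, one-sided α = 0.025, pass at 89 or more. P(X ≥ 89 | 140, 0.55) = 0.0247 and P(X ≥ 89 | 140, 0.68) = 0.887. The stated rule and the stated power above 88% reproduce. So does enrolment: 140/(1 − 0.065) ≈ 150.
- Safety: goal 15%, expected 8.5%, n = 150, one-sided α = 0.05, pass at 15 or fewer. P(X ≤ 15 | 150, 0.15) = 0.0493 and P(X ≤ 15 | 150, 0.085) = 0.794, against a stated 80%. The rule reproduces and the power is within rounding.

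The sample-size arithmetic is sound. Neither calculation allows for selection on the outcome.

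**2. Which treated patients each item can remove.**

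| Item | Patient it could remove | Overlap with a primary endpoint |
|---|---|---|
| No. 5 and the screening log | Survivor of a post-operative stroke who is able to consent | Safety event, if procedure-related and within 30 days |
| No. 16 | Patient given an antiarrhythmic after surgery for another arrhythmia | Performance failure, if flutter or atrial tachycardia counts as another arrhythmia and the drug is a new Class I/III agent or above the previously failed dose |
| No. 3 | Patient with untreated flutter and, read strictly, symptomatic ventricular arrhythmia as well | Performance failure, but a small group |

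**3. Size, safety.** Let *e* be the share of all treated patients who had a primary-event stroke and were removed. The enrolled MAE rate is (0.15 − e)/(1 − e) when the true rate is at the goal.

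| e (assumed) | Share of all MAEs (e/0.15) | Enrolled MAE rate | P(X ≤ 15 of 150) |
|---|---|---|---|
| 0 | 0 | 15.0% | 4.9% |
| 0.5% | 3.3% | 14.6% | 6.5% |
| 1% | 6.7% | 14.1% | 8.6% |
| 2% | 13.3% | 13.3% | 14.4% |

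**4. Size, performance.** Let *e* be the share of all treated patients who would have been failures and were removed. The enrolled responder rate is 0.55/(1 − e) when the true rate is at the goal.

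| e (assumed) | Share of all failures (e/0.45) | Enrolled responder rate | P(X ≥ 89 of 140) |
|---|---|---|---|
| 0 | 0 | 55.0% | 2.5% |
| 1% | 2.2% | 55.6% | 3.3% |
| 3% | 6.7% | 56.7% | 5.9% |

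The values of *e* are assumptions chosen to show the range. The documents give none.

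**The case against.** **The intent is plainly pre-operative.** Inclusion/exclusion sits under Baseline in Section 6.2.2 and in the schedule of events, and Section 7.2 defines a pre-existing condition as one present before the index procedure and reported as medical history. On that view a day-5 stroke is an adverse event, not history. This is a fair reading, and many sites may adopt it. It does not settle the matter. The schedule puts consent in the same Baseline row although consent comes at 12 to 24 months, and exclusion 25 concerns re-intervention since the index surgery, which can only be judged afterwards. Section 7.2 governs adverse-event reporting, not eligibility. With up to 20 sites, either reading may be applied.

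**The screening log does not prove that no. 5 reaches post-operative stroke.** It lists stroke separately from failing the criteria. That is correct, and a reader should not infer the sponsor's intent for no. 5 from it. But the log wording is a second route to the same loss, and it makes no exception for patients able to consent.

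**No. 3 joins its conditions with *and*.** This stands. A reader might infer that every patient whose arrhythmia recurred as untreated flutter is excluded; literally, flutter alone does not meet the criterion.

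**No. 16 may not touch the target arrhythmias.** The endpoint, the non-reportable list in Section 7.6 and a heading in Appendix III all group AF, flutter and atrial tachycardia, so *another* may mean something outside that group. This largely stands: the overlap exists on one reading only, and drug use for recurrent AF is not excluded on any reading.

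**The missing anchor is not exceptional.** About 12 of the 25 exclusions carry a time reference (nos. 2, 4, 6, 8–11, 15, 19, 20, 24 and 25), so it would be wrong to say that most do. What matters for nos. 5 and 16 is their overlap with a primary endpoint.

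**Nobody has yet been scored a failure.** Also correct: rhythm and drug failures are defined at the last visit. Since consent and issue of the monitor coincide with that visit, removal beforehand has much the same effect.

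**Conclusion.** The point holds, with stroke as its firm part. Followed as written, the protocol permits a consenting survivor of a procedure-related stroke within 30 days to be screened out of the test that is meant to count that stroke. Removing such patients can only lower the observed MAE rate. The risk to the performance endpoint through no. 16 is real on one reading and less certain; the effect of no. 3 is narrow.

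The size is unknown. Within the illustrated range the false-pass rate at the goal rises from 4.9% to between 6.5% and 14.4% for safety, and from 2.5% to between 3.3% and 5.9% for performance. These figures assume that every removed patient was a primary-endpoint event or failure. A late or unrelated stroke removed by no. 5 is not an MAE, and its removal does not favour the device on safety.

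A reader might push the range further. Removing 10% of treated patients as failures would give a 30.7% false-pass rate, and removing 3% as strokes would give 22.8%. The documents do not support those cases: they would require 10/45 = 22% of all failures and 3/15 = 20% of all MAEs to be removed by these items. Strokes too disabling to allow consent are lost whatever no. 5 says, so they are not part of this point.

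**What to change.** 1. In Section 5.3.3.1 and the Synopsis, state that exclusions 3, 5 and 16 refer to the patient's status before the index ablation procedure.
2. In Sections 3.1 and 5.2.1, remove major morbidity such as stroke as a screen-failure reason for patients able to consent.
3. Add one sentence: no event after the start of the index procedure makes a patient ineligible under these three items.

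Exclusion 25 refers to a post-index event explicitly and is not altered by this change.

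**Cost.** A few words in three criteria and two screening sentences, through a protocol amendment and an update of the screening form. Sample size, decision rules and planned power are unchanged. The downside for the sponsor is that observed success may be slightly lower and the MAE rate slightly higher.

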#### **3.1 Clinical Investigation Procedures and Follow-up Schedule**

Clinical investigation sites that have treated subjects with the CRYOF surgical ablation system will be approached to determine if they are resourced and willing to consent subjects treated within the past 24-months post procedure for rhythm assessment via 24-hr rhythm monitoring.

The goal of this study is to collect data for patients in which the CRYOF device was used to produce a set of lesions that are based upon the standard Cox-Maze III lesion set (hereinafter referred to as “the optimum lesion set”), consisting of the following lesions:

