#### **4.2 Primary Performance Endpoint**

The primary performance endpoint is defined as freedom from any documented AF, AFL, or AT lasting  $>30$  seconds at the last follow-up visit in the absence of Class I or III AADs (with the exception of previously failed AADs at doses not exceeding those previously failed)

The results of the 24-Hour electrocardiographic rhythm monitoring data used for the primary performance endpoint, will be evaluated by an independent core lab thus maintaining objectivity of the primary performance endpoint.

Subjects will be considered primary performance failures if any of the following conditions are observed:

- Any electrocardiographically documented AF, AFL or AT recurrences lasting >30 seconds in duration at the last follow-up visit (by 30 second 12-lead ECG or 24-hours continuous ECG monitoring);
- The use of either new Class I or III antiarrhythmic drugs or doses exceeding previously failed (i.e., prior to ablation) at the last follow-up visit;
- Any subsequent catheter ablation or surgical ablation treatment for AF, AFL or AT following the index surgical AF ablation procedure (except for treatment of right typical atrial flutter).

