## **5.3 Eligibility Criteria**

### **5.3.1 General Eligibility Criteria**

Assessment for general eligibility criteria is based on medical records at the site and interview with a candidate subject. Subjects must meet ALL of the inclusion criteria to be considered for the clinical investigation. If ANY of the exclusion criteria are met, the subject is excluded from the clinical investigation and cannot be enrolled.

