**GENERAL DISORDERS AND ADMINISTRATION SITE CONDITIONS**

**Atypical Chest Pain:** Located under the sternum, left chest, abdomen, back, or arm and is fleeting or sharp. It is unrelated to exercise, not relieved by rest or the administration of nitroglycerin.

**Drug Reactions:** An unwanted or harmful side effect experienced following the administration of a drug or combination of drugs and is suspected to be related to the drug.

**Fatigue/Malaise:** Weariness, tiredness, or lack of energy. Generalized feeling of discomfort, illness, or lack of well-being.

**Fever:** A temperature  $> 101^{\circ}\text{F}$  not related to a culture positive infection.

**General Discomfort:** Physical or psychosocial signs or symptoms commonly associated with hospitalization that are investigated and determined to require minor (i.e., aspirin, non-narcotic medication) or no treatment.

**Medication Reaction:** An unwanted or harmful side effect experienced following the administration of drug or combination of drugs and is suspected to be related to the drug.

**Multi-organ failure:** Failure of more than one organ due to shock or sepsis. This requires volume and inotropic support and has a high incidence of death.

**Nausea:** The unsettling feeling in the stomach that accompanies the urge to vomit.

**Non-ischemic Chest Pain:** Any discomfort in the chest, shoulder, back or chest wall for which a cardiac ischemic origin is ruled out or not suspected. May be cardiac (for example pericardial) or non-cardiac (for example gastrointestinal) in origin.

**Pain at Catheter Insertion Site:** Pain at access site determined to be associated with the device or procedure.

**Pain:** Reports of pain, ranging from mild discomfort to acute agony, may be generalized or localized, requiring treatment or intervention.

**Peripheral Edema:** is the swelling of tissues, usually in the lower limbs, due to the accumulation of fluids.

**Reoperation:** A repeat operation for the same condition in the same subject or to resolve an adverse event resulting from the initial operation. Reoperation is not an adverse event – it is an outcome – the reason for reoperation is the adverse event.

**Sudden Death:** Cardiac arrest which is unexpected and occurs within minutes of the onset of symptoms.

**Death:** All-cause mortality. Death is not an adverse event, it is an outcome. The Adverse Event is what caused the death.

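### Exclusion 25 screens out, before consent, patients whose repeat surgical ablation section 4.2 would count as a primary performance failure

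*Combined protocol and SAP*

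**What the plan says.** Exclusion 25 appears in the synopsis and in section 5.3.3.1. It bars "Cardiac surgical re-intervention since the index cardiac surgery with concomitant AF ablation procedure", with no limit on purpose, type or timing. Section 5.3.1 gives the consequence: "If ANY of the exclusion criteria are met, the subject is excluded from the clinical investigation and cannot be enrolled".

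Under section 6.1, chart review against the criteria comes before the approach to the patient. Under section 5.2.1, only patients who meet no exclusion are asked to consent. On timing, section 6.2.1 states "Subjects will be consented 12 to 24 months post procedure", and the rhythm monitor is provided at that point.

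Section 4.2 and the synopsis list as a primary performance failure "Any subsequent catheter ablation or surgical ablation treatment for AF, AFL or AT following the index surgical AF ablation procedure". The one carve-out there is for right typical flutter.

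The term used in exclusion 25 is not defined. The nearest entry in Appendix III is Reoperation: "A repeat operation for the same condition in the same subject or to resolve an adverse event resulting from the initial operation". Exclusion 25 neither uses nor cites that entry.

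**The concern.** The entry rule and the endpoint rule treat the same event differently, and the entry rule acts first. Eligibility is settled after most of the outcome period has passed, so the criterion is applied when the re-intervention is already known. A patient whose ablation failed and was redone by cardiac surgery is removed. A patient whose ablation failed and was redone by catheter is kept and counted as a failure.

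This is a single-arm study judged against a fixed 55% goal, so no control arm shares the selection. Each performance failure removed at screening raises the observed responder rate.

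**Working it through.** **Does the same event meet both rules?** Take a patient who has a repeat surgical ablation for AF, done by cardiac surgery, nine months after the index operation and before consent.
- Section 4.2: performance failure.
- Exclusion 25 with section 5.3.1: not enrolled.
- Order of steps (sections 5.2.1, 6.1, 6.2.1): chart review, then approach, then consent. The exclusion decides and the failure is never counted.

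**Does anything in the supplied text restore the patient?**
- The random invitation order in section 3.2 addresses temporal bias. The exclusion still applies to everyone selected.
- Section 8.1 defines the ITT population by device use, but a patient who was never enrolled supplies no data.
- Section 8.8 concerns missing data, and a screened-out patient is not a missing observation.
- Sections 3.1 and 5.2.1 log screen-failure reasons in the EDC, but no analysis of them is described.

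**The plan's own figures first.** Inputs from sections 8.2.1 and 8.3: goal 0.55, expected rate 0.68, 140 evaluable subjects, one-sided alpha 0.025, exact binomial test.
- P(X ≥ 88 | 140, 0.55) = 0.0365, above 0.025.
- P(X ≥ 89 | 140, 0.55) = 0.0247, so the cut-off is 89/140, as stated.
- P(X ≥ 89 | 140, 0.68) = 0.8868, which agrees with the stated power of more than 88%.

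**Illustration.** Let r be the share of treated patients barred by exclusion 25, and f the fraction of those who would be performance failures. The documents give neither, so both are assumptions. With a true responder rate of 0.55 among all treated patients, the rate among those left to enrol is

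p = (0.55 − r(1 − f)) / (1 − r),

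and the chance of passing is P(X ≥ 89 | 140, p).

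| r | f | p | Chance of passing |
|---|---|---|---|
| 0 | – | 0.5500 | 0.0247 |
| 0.1% | 1 | 0.55/0.999 = 0.5506 | 0.0255 |
| 0.5% | 1 | 0.55/0.995 = 0.5528 | 0.0287 |
| 1% | 1 | 0.55/0.99 = 0.5556 | 0.0333 |
| 1% | 0.45 | 0.5445/0.99 = 0.5500 | 0.0247 |
| 1% | 0 | 0.54/0.99 = 0.5455 | 0.0191 |

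**Break-even.** The rate is unchanged when the barred patients fail as often as everyone else: f = 1 − 0.55 = 0.45 with the true rate at the goal, or f = 1 − 0.68 = 0.32 at the expected rate. Above that fraction the exclusion favours the device, and below it the exclusion works against the device.

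**At the cut-off.** Adding back one barred failure to 89/140 gives 89/141, and P(X ≥ 89 | 141, 0.55) = 0.0312, above 0.025. One patient can change the result if the study finishes on the boundary.

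**The case against.** The strongest reply is that the effect is probably small and its net direction unknown. The documents give no re-intervention rate, so every figure beyond the plan's own is assumed. Repeat catheter ablation, the other half of the failure rule, is untouched. Excluding later unrelated cardiac surgery is defensible, because such surgery can itself affect rhythm. The separate SAP mentioned in section 8 was not among the documents, so a sensitivity analysis may exist there. All of this stands and limits the weight of the point. It does not remove the conflict between exclusion 25 and section 4.2.

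Three stronger readings are tempting, and the documents do not support them.

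- *The safety endpoint is biased too.* A reader might infer this from the Reoperation entry in Appendix III, under which an operation for an ablation-related bleed would count. Exclusion 25 does not use that term, and a narrower reading, limited to later separate cardiac surgery, is equally open. Only events related to the ablation procedure or device are MAEs under section 4.1. This is a question of definition.
- *The bias must favour the device.* It does so only if the barred patients fail more often than the rest.
- *The surgical part of the failure rule can never operate.* Section 3.1 speaks of sites willing to "consent subjects treated within the past 24-months post procedure", section 6.1 covers patients treated with the device "and who are within 24-months post-procedure for study eligibility", and neither sets a 12-month minimum. Section 6.2.1 also contains the phrase "Regardless of when the subject is consented". A surgical ablation after an earlier consent would still count. The loss is confined to re-interventions before consent.

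**Conclusion.** The point holds for the primary performance endpoint. As written, exclusion 25 removes a pre-consent repeat surgical ablation that section 4.2 would count as a failure, and the supplied statistical section describes nothing that puts it back. The conflict follows from the text alone and needs no assumption about rates.

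The size is unknown and may be small. If only true failures are barred and the true rate is at the goal, the chance of wrongly passing moves from 2.5% to 2.6% at an assumed 0.1% barred and to 3.3% at an assumed 1%. If the exclusion also bars patients who would not have failed, the net effect shrinks or reverses. The plan's cut-off and power reproduce and are not in dispute. The change should be made, but the point does not by itself undermine the study.

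**What to change.** 1. In the synopsis and section 5.3.3.1, reword exclusion 25 so that a repeat surgical ablation for AF, AFL or AT does not bar entry and is counted as a failure under section 4.2, keeping that section's exception for right typical flutter. Sites can read this fact from the chart without judging relatedness.
2. Define the re-intervention term by procedure type and timing, and not by endpoint status or relatedness. Adjudication comes after eligibility, so a definition based on relatedness would make sites pre-judge it. State whether early re-exploration after the index operation is covered, and how the term relates to Reoperation in Appendix III.
3. From the EDC screening log (sections 3.1 and 5.2.1), report the number of exclusion-25 screen failures and the reason for each.
4. Add a sensitivity analysis of the primary performance endpoint that counts logged repeat surgical ablations as failures, and a bounding analysis that counts all exclusion-25 cases as failures.

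The cost is a wording change in two places, one definition and two short analyses. The observed responder rate may be slightly less favourable. Unrelated cases that stay barred leave a small bias against the device: if 1% are barred and none would have failed, the chance of passing at a true rate of 55% falls from 2.5% to 1.9%. Log detail may be thin, because section 5.1 requires consent before study data are collected, and section 5.4 keeps only minimal data on subjects who consent and then prove ineligible.
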